NSH 1432 PROTOCOL

TITLE

Continuous Monitoring Using a Smart Implantable Device to Compare Medial Parapatellar vs. Subvastus Approaches in Early Post-Operative Total Knee Arthroplasty Recovery

PRINCIPAL INVESTIGATOR

[name]

AUTHORS

[name], [name], [name],

SPONSOR

None

INTRODUCTION

Total knee arthroplasty (TKA) is a highly effective intervention for end-stage knee arthritis, with two common surgical approaches: the Medial Parapatellar (MPP) approach and the Subvastus (SV) approach. Both techniques demonstrate similar long-term outcomes (6 months and beyond) in terms of functional scores, range of motion (ROM), and patient satisfaction, as documented in numerous studies. A key limitation in the literature, however, is the lack of day-by-day data on functional recovery and gait parameters in the crucial first 30 days post operatively - an important period when patients are regaining independence and returning to daily activities.

Persona IQ (Zimmer Biomet) is an FDA-approved smart knee implant that captures continuous, real-world gait data (ROM, step count, stride length, walking speed, etc.) directly from the tibial implant. Unlike external wearables, PIQ provides objective, high-frequency metrics directly from the implant¹. By leveraging PIQ technology in combination with step-tracking wearables, this prospective study aims to fill the current gap by providing daily metrics about the patients pre-operatively and their recovery trajectories during the first 30 days post-operatively and correlating this data with standard PROMs. In this study, patients will be enrolled before surgery and followed longitudinally.

We hypothesize that the SV approach will demonstrate a quicker return to functional milestones in the early post-operative period compared to the MPP approach, even if long-term outcomes have no significant difference. Specifically, we anticipate improved gait metrics (ROM, step count, walking speed) and PROMs (KOOS Jr., NPRS & VR-12) from post-op day 1 to 30 in the SV group compared to the MPP group. The main primary outcome of this study will be step count. This study has the potential to enhance surgical decision-making and optimize rehabilitation protocols by identifying the approach that accelerates early functional recovery.

REVIEW OF LITERATURE

Existing studies comparing MPP and SV approaches typically report outcomes at discrete time points - post-operative day 1, week 4, month 3, and beyond²⁻⁵. These studies consistently demonstrate no significant differences in functional outcomes at 3 or 6 months and beyond post operatively²⁻⁹. They lack data, however, on recovery during the initial stages of TKA post operative recovery, a period when patients are most vulnerable to functional impairments, pain, and difficulty resuming daily activities. While a 2024 prospective study reported significantly improved early outcomes in the SV group compared to MPP at 1 and 3 months, it did not include continuous or real-time data within the first 30 days post-op, leaving this gap in our understanding of recovery during this critical period⁵.

Smart technology, including PIQ can bridge this gap by capturing continuous gait metrics, providing a view of early recovery. Prior studies using external devices (Fary et al., 2023) demonstrated the feasibility of passive gait monitoring but lacked implant-based validation. Persona IQ offers a unique opportunity to directly measure *in vivo* knee kinematics and gait parameters through the recovery period.

Study Design

This is a single-institution, prospective randomized study. Patients of [name], [name], and [name] undergoing primary total knee arthroplasty (TKA) at the Advanced Center for Joint Surgery (Sandy Springs, GA; Cumming, GA) will be screened for eligibility and approached during their pre-operative clinic visits. We plan to enroll 100-120 eligible once obtaining informed consent. For two weeks prior to surgery, enrolled patients will be asked to track their step count using the built-in iPhone Health application. If a patient routinely wears an Apple Watch or similar device, the step count data from the watch may also populate the iPhone Health application and will therefore contribute to the recorded step count. Patients will self-report their average daily step count on the day of surgery by showing the data from the application to research fellows. While recording step count, adherence will be recorded as the number of days with available iPhone Health data meeting validity criteria (≥ 500 steps). Days with 0–499 steps will not be considered valid unless the patient attests to medically-indicated low activity, in which the reason will be documented.

During surgery, all patients will receive a Zimmer Persona IQ utilizing a medial congruent bearing with a posterior cruciate ligament (PCL) sacrifice. All patellas will be resurfaced as well. This standardized implant choice was made to reduce variability and allow for direct comparison of functional outcome between surgical approaches. PIQ data will be accessed using the Canary Medical database. Patients will be followed for a minimum of 6 months post-operatively, during which they will complete digital patient-reported outcomes.

The surgical approach, MPP or SV, will be randomly assigned with an equal chance of receiving either. This randomization will be stratified by sex and age.

Inclusion Criteria:

- All patients older than 18 years of age who plan to undergo medial congruent polyethylene bearing primary TKA with a PIQ
- Eligible for both approaches
- Have an iPhone and willing to “wear” it for two weeks preoperatively to get an estimated average stepcount

- Provide informed consent
- Willing to complete follow ups

Exclusion Criteria:

- Patients with TKA revisions
- Patients with insufficient pre-operative range of motion in the operative knee (flexion contracture of > 20 degrees or < 90° of knee flexion)
- Patients with Contralateral TKA within study time frame
- Patients with TKA other than medial congruent polyethylene bearing
- Patients with bilateral surgery
- Patients without a valid and active email address
- Patients not willing or able to participate in study and follow-ups
- Patients who use assisted devices to ambulate
- Rheumatoid arthritis

Primary outcomes:

- Preoperative data
 - Preoperative goniometric functional range of motion
 - Step count
 - Pre-Operative Step Count via Force Therapeutics
 - In cases where pre-operative step count is missing or incomplete, patients can update force or discuss what range of activity they are classified in based on step count
- Continuous PIQ Data
 - Tibial ROM
 - Cadence
 - Walking speed
 - Stride length
 - Step count
 - Distance
- 6 week follow up data
 - Goniometric functional range of motion

Secondary outcomes:

- Time to achieving key milestones in daily activities (e.g. ability to perform basic household tasks such as taking out the trash)
- Veterans Rand 12-Item (VR-12) Health Survey (Preop, 6 weeks, 6 months)
- Procedure Satisfaction (6 weeks, 6 months)

- Numeric Pain Rating Scale (NPRS) (Force data)
- KOOS, JR. (Knee injury and Osteoarthritis Outcome Score for Joint Replacement) - Preop, 6 weeks, and 6 months
- Forgotten Joint Score - Preop, 6 weeks, 6 months

Other measures:

- Patient Demographics including
 - Age
 - Sex
 - Body Mass Index (BMI)
 - American Society of Anesthesiologists (ASA) score
- Surgical side (L/R)
- Comorbidities

ANALYSIS

Post-operative functional data will be extracted from the Canary Medical platform for all Persona IQ participants. Preoperative step count will be collected from each participant's iPhone. Descriptive and comparative statistical analyses will be conducted using this real-time data.

[figure not shown]
Data are broken down descriptively first to understand the distribution of the medial parapatellar and subvastus groups. Continuous data are presented as mean (standard deviation) and categorical data are presented as cell count (%). Shapiro-Wilks and Kolmogorov-Smirnov tests are used to assess the normality of the continuous data. T-tests are used to calculate P values for continuous data and Chi-squared tests are used to calculate P values for categorical data. Following this, an unadjusted and adjusted logistic regression are analyzed using PROMs as the dependent outcome. Significance is determined at P value < .05. All statistical analyses are done using R Studio (version 4.3.1, Vienna, Austria). Using a significance level of 5%, a power of 80% and an effect size of 0.3, we believe that 55-60 patients are needed for the MPP group and 55-60 patients are needed for the SV group to determine a difference of 1000 steps per day.

CONSENT PROCEDURE

Subjects will be identified via the surgical schedule and contacted during their pre-operative clinic visits. A research coordinator will explain the study and obtain informed consent. No study activities (e.g., device usage or data collection) will begin prior to consent. Patients may withdraw at any time.

COST AND COMPENSATION

As this is currently standard of care at Northside Hospital, no compensation will be given.

CONFIDENTIALITY OF DATA

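### The planned enrolment of 100-120 does not match the 110-120 patients (55-60 per group) that the protocol says it needs, and no allowance for loss is described

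*Protocol*

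**What the plan says.** The Study Design section gives the recruitment figure: "We plan to enroll 100-120 eligible once obtaining informed consent". Enrolment is thus tied to consent. The same section then asks enrolled patients to track their steps for two weeks before surgery.

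The approach is "randomly assigned with an equal chance of receiving either", so allocation is 1:1.

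The Analysis section gives the requirement. "Using a significance level of 5%, a power of 80% and an effect size of 0.3", the authors write, "we believe that 55-60 patients are needed for the MPP group". The other group has the same figure: "55-60 patients are needed for the SV group to determine a difference of 1000 steps per day".

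The Consent Procedure section adds: "Patients may withdraw at any time".

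The protocol gives no expected loss, no inflation of the sample size for loss, and no statement on whether patients who leave before surgery are replaced. It does not say when randomisation takes place.

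**The concern.** Two current sections state the size of the trial, and they differ. Recruitment could end anywhere from 100 to 109 patients in full compliance with the Study Design section, and the trial would then be smaller than the Analysis section says is needed for step count, which the Introduction names as the main primary outcome.

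Beyond that, the recruitment range has no margin above the requirement. Its upper end, 120, equals the upper end of the stated need. A patient who consents but withdraws, has surgery cancelled or does not receive the implant contributes no post-operative implant step count. Any such loss comes straight off a number that at best matches the requirement.

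**Working it through.** **Inputs from the protocol.** Enrolment 100-120 (Study Design). Need 55-60 per group, significance level 5%, power 80%, effect size 0.3, difference 1000 steps per day (Analysis). Allocation 1:1 (Study Design). No loss rate is given, so the rates below are assumptions.

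**The plan's own figure.** Reading 0.3 as a standardised mean difference d with a two-sided test, n per group = 2(1.960 + 0.842)² / d² = 2 × 7.85 / 0.09 ≈ 174.4, so 175 per group; a one-sided test gives 138. The stated 55-60 is not reproduced. That is a separate question. The rest of this check takes 55-60 as the protocol's stated requirement and asks only whether the enrolment range meets it.

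**Enrolment against need, no loss.**
- Need: 2 × 55 = 110 to 2 × 60 = 120.
- 100 enrolled: 100 / 2 = 50 per group, 5 below 55 (5/55 = 9%) and 10 below 60.
- 110 enrolled: 55 per group, with nothing to spare.
- 120 enrolled: 60 per group, with nothing to spare against the upper figure.

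**Loss that can be tolerated.** At 120 enrolled, 110 remain if loss is at most 1 − 110/120 = 8.3%, that is, 10 patients.

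**Assumed loss.** Patients left = enrolled × (1 − loss). Enrolment needed = patients wanted / (1 − loss), rounded up.

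| Assumed loss | Left from 100 | Left from 120 | Enrol to end with 110 | Enrol to end with 120 |
|---|---|---|---|---|
| 0% | 100 | 120 | 110 | 120 |
| 5% | 95 | 114 | 116 | 127 |
| 10% | 90 | 108 | 123 | 134 |
| 15% | 85 | 102 | 130 | 142 |

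At 10% loss or more, no enrolment figure in the planned range leaves 110.

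**What the shortfall would cost in power, if 55-60 were right.** The difference that gives 80% power at n per group is d = 2.802 × √(2/n): 0.534 at n = 55 and 0.511 at n = 60. Power at a smaller n is Φ(d√(n/2) − 1.960), two-sided 5%.

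| Patients per group | If 55 gives 80% (d = 0.534) | If 60 gives 80% (d = 0.511) |
|---|---|---|
| 50 (100 enrolled, no loss) | 76.2% | 72.5% |
| 45 (100 enrolled, 10% loss) | 71.7% | 67.9% |

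**The case against.** The ranges overlap from 110 to 120, and changing 100 to 110 removes the direct contradiction. The loss argument rests on assumed rates: a right to withdraw is not evidence that patients will. Patients are found through the surgical schedule, already plan this operation with this implant, and have their post-operative steps recorded by the implant itself. At 120 enrolled and 5% loss, 114 remain, which is above 110. All of this stands. It limits the severity, but it does not reconcile 100-109 with a stated minimum of 110.

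Several stronger readings are tempting, and the protocol does not support them.
- A reader might infer that patients who leave are not replaced. The protocol is silent on replacement, and gives no rule for counting patients who leave before surgery. All that can be said is that neither replacement nor a loss allowance is described.
- A reader might treat the two weeks of step tracking as a run-in that removes patients. It is baseline measurement. No rule drops a patient for poor adherence, and the outcome list lets a missing or incomplete count be filled in later or replaced by an activity range.
- A reader might conclude that the enrolment range cannot deliver 55 per group. It can, if recruitment runs to 120 and loss stays within 8.3%.
- A reader might call for randomisation on the day of surgery. No randomisation time is stated, so none is shown to be wrong. Moving it would be a design preference.

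The larger weakness of the sample size paragraph is that 55-60 does not follow from an effect size of 0.3. Resolving that may replace both numbers, so the present mismatch is secondary.

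**Conclusion.** The point holds as an inconsistency between two sections. The lower end of planned enrolment falls 10 patients short of the lower end of the stated need, which is 5 per group. This part needs no assumption beyond the 1:1 allocation that the protocol states.

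The absence of a margin for loss is also plain from the figures, but its effect depends on a loss rate that the protocol does not give. At an assumed 5% the range leaves 95-114 patients, and at 10% it leaves 90-108. The power figures are conditional on 55-60 per group giving 80% power, which the protocol's stated inputs do not reproduce. They show the size of the shortfall on the protocol's own terms and are not estimates of the trial's actual power.

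This is a correction to make for consistency, and it ranks below the defects that must be fixed before the trial can be relied on.

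**What to change.** Make Study Design and Analysis agree, in one of two ways.

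1. State the Study Design target as 110-120 patients randomised and operated, so that the lower bound rises from 100 to 110, and let the number consented exceed this by an explicit loss allowance. To end with 110, that means consenting 116 at an assumed 5% loss or 123 at 10%. This is a recruitment count and should not be read as defining who is analysed.
2. Keep 100-120 consented, and state in Analysis both the number per group expected after a named loss rate and the power that number gives. At 10% loss the number is 45-54 per group. Giving the smaller number without its power would hide the shortfall.

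The first option costs a line of wording and recruitment of at least 10 more patients at the lower end, plus whatever covers loss. The second costs wording and a lower stated power. Either should be done in the same revision that settles how 55-60 per group relates to the effect size of 0.3, because that answer may change the requirement itself.

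### Surgeon is neither a stratification factor nor a term in the stated step-count comparison, so a chance surgeon imbalance goes uncorrected and some precision is lost

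*Protocol*

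**What the plan says.** - **Source of patients (Study Design).** The trial screens "Patients of [name], [name], and [name] undergoing primary total knee arthroplasty (TKA" at two locations of one centre, Sandy Springs and Cumming. The text does not call the three individuals surgeons. That is an inference, though the natural one.
- **Allocation (Study Design).** "The surgical approach, MPP or SV, will be randomly assigned with an equal chance of receiving either". The next sentence is "This randomization will be stratified by sex and age". Neither surgeon nor location is named as a factor, and no age bands or block sizes are given.
- **Main outcome (Introduction).** "The main primary outcome of this study will be step count".
- **Analysis.** "T-tests are used to calculate P values for continuous data". Step count is continuous, so this is its stated test, and it has no covariates. The only adjusted analysis is a logistic regression of the PROMs, whose covariates are not named.
- **Data collected (Other measures).** Age, sex, BMI, ASA score, side and comorbidities are listed. The operating surgeon is not.

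**The concern.** The intervention is a surgical technique, so the operator is part of how it is delivered. Surgeon may carry differences in proficiency, case mix and post-operative instructions, any of which could affect steps in the first 30 days. The protocol gives no data on these. It does fix the implant, bearing, PCL handling and patellar resurfacing in order to limit variability, but leaves out the operator, an obvious remaining source.

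Two things are at stake. If one surgeon happens to do noticeably more of one approach, part of that surgeon's effect enters the approach difference and the t-test does not remove it. Even when the split is even, between-surgeon variation inflates the standard error.

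**Working it through.** The protocol gives no figure on surgeon, so there is none to reproduce. Its sample-size statement is a separate matter and is used here only for the group size (55-60 per arm) and the effect size (0.3).

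**Assumptions not in the documents:** 120 patients, 40 per surgeon; allocation unrelated to surgeon; surgeon explains a share v of step-count variance, with v = 5-15%.

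**1. Chance of an uneven split, arm totals free.** Each surgeon's SV count is Binomial(40, 0.5).
- 60:40 or worse means a count of 16 or fewer, or 24 or more: probability 0.268. At least one of three surgeons: 1 - (1 - 0.268)^3 = 0.61.
- 65:35 or worse means 14 or fewer, or 26 or more: probability 0.081. At least one of three: 1 - (1 - 0.081)^3 = 0.22.
- 95% range for one surgeon: 14:26 to 26:14.

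**2. The same, arms fixed at 60:60.** The probability of SV counts (a, b, c) with a + b + c = 60 is C(40,a)·C(40,b)·C(40,c) / C(120,60). Summing over the relevant counts:
- at least one surgeon 60:40 or worse: 0.36;
- at least one surgeon 65:35 or worse: 0.08;
- 95% range for one surgeon: 15:25 to 25:15.

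The protocol plans groups of equal size but does not describe blocking, so the truth lies between the two cases.

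**3. Unequal caseloads.** With assumed shares from equal thirds to 60/30/10, equal arms and N = 100-120, simulation gives the chance that some surgeon's share differs between arms by at least 10 percentage points as about 39-64%. For at least 15 points it is 13-26%, and for at least 20 points 6-11%.

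**4. Effect on the estimate, arms fixed at 60:60.** Let the surgeon effects be -s, 0 and +s in SD units. Their variance is (2/3)s², so s = √(1.5v): 0.274 at v = 5% and 0.474 at v = 15%. If the two outer surgeons contribute a and c SV patients, the arm difference shifts by 2s(c - a)/60. From the distribution in step 2, |c - a| is 9 or more with probability 0.058, about one allocation in twenty.
- v = 5%: 2 × 0.274 × 9/60 = 0.08 SD.
- v = 15%: 2 × 0.474 × 9/60 = 0.14 SD.

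Against the protocol's effect size of 0.3 these are 27% (0.08/0.3) and 47% (0.14/0.3).

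**5. Precision.** Removing a share v of the variance is worth 1/(1 - v) - 1 more patients: 5% at v = 5% and 18% at v = 15%. At 60 per arm the standard error falls from √(2/60) = 0.183 SD to 0.178 SD (v = 5%) or 0.168 SD (v = 15%). For v = 1-10%, two-sided power at an effect size of 0.3 moves from 35% to 35-38% at 55 per arm, and from 38% to 38-41% at 60 per arm.

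**The case against.** **The t-test is valid without surgeon.** This stands. Randomisation makes the comparison unbiased on average, and the t-test's standard error already carries the between-surgeon variation. A reader might infer that surgeon confounds the comparison. The documents do not support that: the problem is chance imbalance in the one allocation realised, plus lost precision.

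**The choice of strata is a judgement.** This also stands. Few strata are sensible with 100-120 patients, and stratifying by sex and age is legitimate. Leaving surgeon out of the strata would not be a finding on its own.

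**Covariates belong in the SAP, which is not shown.** This stands in part. A SAP may name further covariates. But the protocol does not leave the step-count comparison open: it states a t-test. For the PROMs the objection holds fully. An adjusted regression is planned with unnamed covariates, so one can say only that no surgeon term is specified. A reader who concludes that the trial adjusts for surgeon nowhere goes further than the text.

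**The imbalance figures can be overstated.** Correct. The 61% and 22% hold only if arm totals drift freely. With arms fixed at 60:60 they are 36% and 8%, so only the ranges should be cited.

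**The gain is modest and its mechanism unproven.** The power gain is a few percentage points, and nothing in the documents supports a particular surgeon share. One institution and a standardised implant remove some variation, though not differences between operators. A main effect for surgeon also does not deal with a surgeon who is better at one approach than the other. That is an interaction, and neither this term nor stratification removes it.

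**Conclusion.** The point holds as a precision and robustness issue for step count. Surgeon is absent from both the stratification and the stated test, so a chance imbalance would go uncorrected and between-surgeon variation stays in the error.

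Under equal caseloads, at least one surgeon is split 60:40 or worse in about 36-61% of allocations, and 65:35 or worse in about 8-22%. With surgeon at an assumed 5-15% of variance, adjustment is worth about 5-18% more patients. With arms at 60:60 and evenly spaced surgeon effects, about one allocation in twenty shifts the difference by 0.08-0.14 SD or more.

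These sizes rest on the assumed caseloads and variance share, and on reading the three individuals as the surgeons. The change is worth making because it is cheap, not because the planned test is invalid.

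**What to change.** 1. Add the operating surgeon to the recorded variables.
2. Replace the step-count t-test with a linear model, on the same per-patient step-count measure, containing approach, surgeon (fixed effect), sex, age and baseline steps. Specify it before the outcome data are examined. Sex and age belong there in any case because they are stratification factors.
3. State how a missing baseline count enters the model, since the protocol already expects some.

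**Cost:** one model term and one data field. Surgeon takes two degrees of freedom. With one each for approach, sex, age (entered as continuous) and baseline steps, plus the intercept, the model uses seven, leaving 93-113 residual degrees of freedom in 100-120 patients.

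**Optional:** if the allocation list can still be changed, stratify by surgeon too. This is a matter of judgement. With two age bands (assumed, as none are stated), sex × age × surgeon gives 2 × 2 × 3 = 12 strata, or about 8-10 patients each. Stratifying by surgeon and sex, with age kept as a covariate, gives six.

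### Time to daily-activity milestones is a time-to-event outcome, but the only stated rule that fits a duration is mean (SD) with a t-test, which cannot use patients who withdraw or have not reached the milestone

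*Protocol*

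**What the plan says.** The protocol's Introduction states: "We hypothesize that the SV approach will demonstrate a quicker return to functional milestones in the early post-operative period". Under Secondary outcomes it lists "Time to achieving key milestones in daily activities", with a simple household chore as the example. No assessment schedule, time origin or end of observation is given for this outcome, whereas several of the other secondary outcomes carry visit times. Under Study Design, "Patients will be followed for a minimum of 6 months post-operatively".

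The Analysis section gives one general rule. For description, "Continuous data are presented as mean (standard deviation) and categorical data are presented as cell count". For testing, "T-tests are used to calculate P values for continuous data and Chi-squared tests are used to calculate P values for categorical data". The only model named is for other data: "an unadjusted and adjusted logistic regression are analyzed using PROMs as the dependent outcome". No time-to-event method appears, and no rule covers patients who withdraw or have not reached a milestone. The section does not say explicitly which test applies to the milestone outcome.

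**The concern.** A number of days from surgery to a milestone is a duration, so under the general rule it falls in the continuous branch. A patient who has not reached the milestone by the last assessment, or who withdraws first (the Consent Procedure allows this at any time), has no such number. A t-test must then either leave that patient out or use a substituted value, and the protocol states neither. The logistic regression would not help if milestones were counted as PROMs, because it does not handle censored times. The normality tests do not help either: no alternative test is named, and a rank test on achievers alone would face the same gap.

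If SV does speed recovery, more MPP than SV patients will be unreached at any given cut-off. Leaving them out removes the slowest recoverers mainly from the slower arm and pulls the two means together. The estimate is diluted and power is lost, against the direction the investigators expect.

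**Working it through.** **Inputs.** From the protocol: 55–60 per arm, equal allocation, 5% significance and at least 6 months of follow-up. The protocol gives no event rate, hazard ratio, dropout rate or assessment window for milestones, so these are assumed below. Its sample-size figure is for step count. There is no figure for this outcome to reproduce.

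**Step 1: dilution by share not reaching the milestone.** Assume exponential times, a 30-day window and a hazard ratio of 1.7 for reaching the milestone. With c the MPP share not reached by day 30:

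- rate λ = −ln(c)/30; SV share not reached = c^1.7
- true mean difference = (1/λ)(1 − 1/1.7)
- mean among achievers = 1/λ − 30c/(1 − c); in SV, use 1/(1.7λ) and c^1.7
- mean with non-achievers set to day 30 = (1 − c)/λ, likewise for SV

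For c = 0.20: 1/λ = 30/1.609 = 18.64 days in MPP and 18.64/1.7 = 10.965 in SV, with 0.2^1.7 = 6.5% of SV not reached.

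- True difference: 7.68 days.
- Achievers only: 18.64 − 7.50 = 11.14 against 10.965 − 2.079 = 8.89, a difference of 2.25 (simulated 2.30).
- Capped at day 30: 0.8 × 18.64 = 14.91 against 0.9352 × 10.965 = 10.25, a difference of 4.66 (simulated 4.67).

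Simulation with 58 per arm and 1,500 runs per row:

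| MPP not reached | True diff. (days) | Achievers-only diff. | Capped diff. | Power: t-test, achievers | Power: t-test, capped | Power: log-rank |
|---|---|---|---|---|---|---|
| 1% | 2.7 | 2.4 | 2.6 | 78% | 82% | 81% |
| 5% | 4.1 | 2.8 | 3.7 | 65% | 80% | 81% |
| 10% | 5.4 | 2.6 | 4.2 | 47% | 77% | 78% |
| 20% | 7.7 | 2.3 | 4.7 | 31% | 73% | 76% |
| 30% | 10.3 | 1.8 | 4.7 | 20% | 67% | 72% |

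Benchmark for the log-rank column: the Schoenfeld formula gives 4(1.960 + 0.842)²/(ln 1.7)² = 112 events for 80% power. If all 116 patients reach the milestone, power is 81.5%, in line with the first row. With no true difference and equal non-achievement, all three tests reject in 4–6% of runs.

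**Step 2: dependence on the window.** Assume 55 per arm, Weibull times with shape 1.5, MPP median m = 14, 21 or 28 days, and hazard ratio 1.5–1.75. The MPP share not reached by day t is exp(−ln 2 × (t/m)^1.5).

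- *30 days:* for m = 14, exp(−0.693 × 3.137) = 11%; for m = 28, exp(−0.693 × 1.109) = 46%. Power is about 6–51% for the t-test on achievers, 30–77% for the t-test with non-achievers set to day 30, and 36–81% for log-rank. Achievers' means differ by 0.9–2.8 days, against a true difference of about 4–10 days.
- *180 days:* even for m = 28, exp(−0.693 × 16.30) is about 0.00001, so almost everyone reaches the milestone. Power is 51–81% for the t-test and 54–82% for log-rank, a gap of at most about 3 points. With an assumed 10% early dropout the gap is up to about 4 points. The achievers' difference of 3.8–10.1 days shows no visible shrinkage.

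**The case against.** The strongest reply is that two conditions for serious harm are not in the protocol. The first is a 30-day cut-off. The Introduction's 30-day window concerns daily metrics, gait and PROMs, and nothing ends milestone observation there; stated follow-up is at least 6 months. The example task is an easy one, and users of walking aids are excluded, so a large share of non-achievers at 6 months is not supported. The second is the dropping of non-achievers, which is an inference. The capped t-test comes close to log-rank, so most of the loss comes from that assumed handling and not from the t-test itself. Milestones might also be recorded as reached or not reached and tested by chi-squared, and an unseen SAP could override the general rule.

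These replies limit the size of the point but do not remove it. The outcome is worded as a time, the rule that fits a time is the t-test, and no provision is made for a patient without a value.

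A reader might also infer that the test of the trial's own hypothesis is biased toward no difference. The protocol does not support that. Directly after the milestone sentence it spells the hypothesis out through gait metrics and PROMs and names step count as the main primary outcome. The milestone outcome is secondary, and no sample size rests on it.

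**Conclusion.** The point holds in a conditional form. The stated general rule does not suit a time-to-event outcome, and a method that uses every randomised patient is available at little cost. The loss is large only if assessment stops around day 30 and non-achievers are left out; over 6 months with little dropout it is negligible. All magnitudes rest on assumed distributions, medians and hazard ratios, because the protocol gives none. The harm is a diluted estimate and lost power, not false positives under equal censoring. An unconditional claim of bias would go beyond the document. This should be changed, but it does not threaten the primary comparison.

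**What to change.** In the Analysis section, exempt time to milestones from the t-test rule. Analyse each milestone on all randomised patients with Kaplan-Meier curves and a log-rank test or Cox model adjusted for the stratification factors, sex and age. Censor patients who have not reached the milestone at their last assessment. If milestones are asked about only at visits, use an interval-censored method instead. State the milestone definitions, the time origin and the assessment schedule, and name the milestone of main interest.

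The analysis needs only standard software. The cost lies in data capture: the date of the milestone, or of the last assessment, must be recorded for each patient, so this is best settled before data collection.

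These methods also assume that withdrawal is unrelated to recovery, so reasons for withdrawal should be reported by arm.
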